# Introduction

A proper warm-up (WU) has the potential to enhance physical qualities, such as speed, strength and explosiveness, for a better athletic performance in training or competition (Till & Cooke, 2009). Therefore, warming up before training sessions, in addition to giving the athlete a greater physical readiness (Hammami et al., 2016; Thapa et al., 2022), is also an opportunity to mentally prepare themselves for the training contents and induce positive psychological effects, such as strengthening concentration and self-confidence (Bishop, 2003a, 2003b; McGowan et al., 2015).

In most sports, WU aims to increase muscle blood flow, heart rate, overcome viscous resistance to muscle movement, and enhance neurological excitability (Fradkin et al., 2010) in order to prepare the players for an immediate performance (McGowan et al., 2015; van den Tillaar & von Heimburg, 2016) and therefore being able to respond to physically demanding training sessions (van den Tillaar & von Heimburg, 2016; Yanci et al., 2019). To achieve this, previous research have suggested that WU protocols should have static stretching exercises (McMillian et al., 2006; Vazini Taher & Parnow, 2017) and dynamic movements that increase both body temperature and range of motion, enhance motor unit excitability, improve kinesthetic awareness and work on technique by reinforcing critical motor programs (Mann & Jones, 1999; Rutledge & Faccioni, 2001; Thompsen et al., 2007).

More recently, alternative WU protocols, focusing on potentiation methods, have been proposed in the literature (Aloui et al., 2021; Brink et al., 2022; Ciocca et al., 2021; Matusiński et al., 2021) and applied in practice. These methods are characterized by exercises that use the stretching-shortening cycle (Michailidis et al., 2019), that is, the ability of the neural and musculotendinous systems to produce maximum force in the shortest possible time (Wang & Zhang, 2016). To our knowledge, the most common WU protocol exploring the potentiating

effect presented in the literature is the one that resorts to the use of plyometrics (PLY), sprint and change of direction (COD) (Aloui et al., 2021; Michailidis et al., 2019). In potentiation, Post-Activation Potentiation (PAP) and Post-Activation Performance Enhancement (PAPE) are two of the most studied and discussed phenomena. Nevertheless, some differences distinguish these two mechanisms (Prieske et al., 2020)

PAP is associated to an increase in contractile muscle force, in response to maximal voluntary contractions and capable of conditioning subsequent muscle contractions, measured as the maximal contraction force evoked by supramaximal electrical stimulation (Blazevich & Babault, 2019; Prieske et al., 2020). From a physiological perspective, the main mechanism of PAP is the phosphorylation of myosin regulatory light chains (Blazevich & Babault, 2019; Boullosa et al., 2018; Prieske et al., 2020; Tillin & Bishop, 2009). The authors suggest that there is a time window to optimize the PAP, with a recovery period between 7 to 10 minutes (Wilson et al., 2013).

Conversely, PAPE refers to the increase in maximal voluntary strength, power, or velocity (dynamic or isometric) following a conditioning contraction (Prieske et al., 2020). Accordingly, different training protocols have been used to improve the PAPE, such as PLY (Brink et al., 2022), resistance training (Carbone et al., 2020), sprint training (Bevan et al., 2010), the flywheel paradigm (Sañudo et al., 2020) and COD drills (Lockie et al., 2014). Similarly to PAP, the performance enhancing effects may be observed after a resting period, peaking 7-10 minutes after a conditioning contraction (Cuenca-Fernández et al., 2017; Maloney et al., 2014; Tillin & Bishop, 2009; Wilson et al., 2013).

The effectiveness by which a conditioning activity can stimulate the mechanisms that strengthen muscles and improve performance depends on the balance between fatigue and potentiation (Rassier & Macintosh, 2000; Tillin & Bishop, 2009; Wilson et al., 2013). This balance is affected by a variety of factors, including training experience (Prieske et al., 2020),

resting time using an optimal recovery time (Hodgson et al., 2005; Tillin & Bishop, 2009), the intensity of the conditioning activity performed (Sale, 2002), muscle fiber type and gender (DeRenne, 2010). Therefore, optimal performance occurs when fatigue has decreased, and the potentiated effect still exists (Hodgson et al., 2005). Therefore, this study aims to determine if the performance of female football players is affected after the exposure to a potentiation protocol. It is hypothesized that performance in the selected physical tests will improve significantly and meaningfully after performing the chosen potentiation protocol compared to the control group's warm-up.

## Methods

### Trial Design

We will perform a randomized parallel trial in a single highly trained female soccer team (highly trained/national level) (McKay et al., 2022) competing in the Portuguese second division. A convenience sample will be used, due to easy access from one of the researchers, who is employed in the club. One group will receive the experimental intervention (EXPG), which will consist of a potentiation protocol as a WU and the second group will receive the control intervention (CONG) which consists of performing their usual WU exercise program. Each group will be tested before and after performing the WU to which they are assigned. Physical tests and intervention protocol will take place during the competitive period. All training sessions and physical tests will be performed on synthetic grass of the team's field. The tests will be applied without a blinded assessor integrating the technical team. However, due to the use of objective and reliable technology, hardly influenced by knowledge of the interventions to which the participants were allocated, we are confident that the non-blinded of assessors will not have a meaningful impact on the results.

## Participants

Eighteen female soccer players between 16 and 21 years of age will participate in this study. Participants will be randomly allocated between a CONG (n=9) and a EXPG (n=9), using the Excel Software and the Random function and the allocation sequence will be concealed from the main researcher, responsible for the implementation of the protocols, until the beginning of the interventions. The inclusion criteria, to be applied before the randomization process, will consider athletes, from any playing position (except goalkeepers), able to train without limitations. Subjects will be excluded if they have any existing medical conditions that will compromise their participation. All participants will be informed about the purpose and content of the project, as well as the potential risks and benefits of the study, and will sign an informed consent.

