## Interventions

We have stipulated that the intervention will last three weeks. The first week will be a week of familiarization with the physical tests and protocol, requiring two training sessions, before the initiation of the study to accustom themselves to the physical tests and the protocol procedures. During the first week, the familiarization with the physical tests and the protocol will be performed before the training sessions. The protocol intervention will be performed in the following two weeks, in a total of four training sessions (two per week). The collection of data from the physical tests will begin in the second week, the first moment of collection will be at the at the beginning of first training session and the second moment at the end of the third week (after the fourth protocol session has been completed). The duration of each session will be 20 min.

The intervention protocol proposed in the present study was modified from the protocol used by Aloui et al. (2021), and consists of four sets: (i) First set - 6 hurdle jumps (HJ), with a

distance of 70-cm between each, followed by a 15-m sprint with COD; (ii) Second set - 6 lateral HJ (3 to the left and 3 to the right) followed by a 10-m sprint with COD; (iii) Third set - 6 bouncy strides (BC) followed by a 15-m sprint with COD; (iv) Fourth set - 6 broad jumps (BJ) followed by a 10-m sprint with COD. All COD circuits represent different configurations, changing the sprint distance and the angle of the COD curve. In the last set, we replaced the drop jump with the BJ. Due to the drop jumps being done consecutively, there is a component of horizontal resistance, so we chose to implement the BJ, which offers a greater horizontal component (Dello Iacono et al., 2017) and the forces are generated in the same musculature across the hips, knees, and ankles (Svantesson & Grimby, 1995), being a precursor exercise to improved performance in the sprint and COD (Dello Iacono et al., 2017). All repetitions and sets will be separated by 90-s recovery intervals, as well as, each set will have to be performed 3 times (Aloui et al., 2021). It should be noted that it is intended that the participants perform the procedures under study at the same time of day, i.e., same time and temperature as similar as possible. All physical tests and protocol under study are to be performed with the participants wearing their usual soccer shoes.

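### Allocation is balanced only on arm size, so the arms have a 29% chance of starting at least 0.5 SD apart on a given test; pairing on timed week-1 runs would be a cheap, modest improvement

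*Combined protocol and SAP*

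**What the plan says.** The Trial Design section describes a parallel comparison within one team. The Participants section gives the sample: "Eighteen female soccer players between 16 and 21 years of age will participate in this study". It then gives the allocation: "Participants will be randomly allocated between a CONG (n=9) and a EXPG (n=9), using the Excel Software and the Random function". No stratification, pairing or minimisation appears anywhere in the document.

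The draw is not dated. The plan says only that "the allocation sequence will be concealed from the main researcher, responsible for the implementation of the protocols, until the beginning of the interventions".

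The Interventions section puts familiarization first: "The first week will be a week of familiarization with the physical tests and protocol, requiring two training sessions". It does not say that these runs are timed, and it states that "The collection of data from the physical tests will begin in the second week".

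Under Statistical analysis the plan is a mixed repeated measures ANOVA with no baseline covariate.

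**The concern.** With nine players per arm, a single draw that fixes only the arm sizes will often leave one arm visibly faster at pre-test. Neither the allocation nor the stated model does anything specific about that.

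This trial could do better at low cost. All 18 players come from one team and can be listed before allocation, and they meet both tests in week 1, ahead of the week-2 pre-test. If those runs were timed, similar players could be paired and split at random. Because all pairs would be drawn at once, nobody could guess the next assignment from earlier ones.

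At stake are the face validity of one small result and a little precision. The validity of the randomisation is not in question.

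**Working it through.** The plan gives no power, sample-size or imbalance figure, so there is nothing of its own to reproduce.

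**Inputs from the plan.** 18 players, 9 per arm; two tests (T-test and 40-m sprint); arm size the only restriction.

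**Assumed, because the plan gives no figure.** Normal test times; the correlation between week-1 and pre-test times; the correlation between the two tests; the pre-post correlation.

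**1. One test, free draw.** SE of the difference in arm means = SD × √(1/9 + 1/9) = 0.471 SD. P(gap ≥ 0.5 SD) = 2 × [1 − Φ(0.5/0.471)] = 2 × [1 − Φ(1.061)] = 28.9%. Simulation gives 28.9% with the population SD and 30.5% with the observed pooled SD. A gap of 1 SD or more has probability 3.4%.

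**2. At least one of two tests, free draw (bivariate normal).** 49% if the pre-test times are uncorrelated, 48% at correlation 0.3, 46% at 0.5, 43% at 0.7 and 37% at 0.9. Moderate correlations give the 44-48% used here.

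**3. What a gap does to the planned comparison.** The group-by-time term compares changes, so a constant gap cancels. What remains is regression to the mean, expected to be (1 − r) × 0.5 SD for a 0.5 SD gap and pre-post correlation r:

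- r = 0.9: 0.1 × 0.5 = 0.05 SD
- r = 0.7: 0.3 × 0.5 = 0.15 SD

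With equal SDs, the SE of the change contrast is 0.471 × √[2(1 − r)], which is 0.211 SD at r = 0.9 and 0.365 SD at r = 0.7. The shifts are therefore 0.05/0.211 = 0.24 and 0.15/0.365 = 0.41 of a standard error.

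**4. Pairing on the composite.** Players are ranked on the two standardised week-1 times combined, nine adjacent pairs are formed, and assignment is random within pairs. One set of simulations (200,000 draws each) gave:

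| Between-test correlation (true scores) | Week-1 to pre-test correlation | Gap ≥ 0.5 SD, given test | At least one test | At least one test, free draw |
|---|---|---|---|---|
| 0.5 | 0.8 | 14% | 26% | 48% |
| 0.5 | 0.9 | 10% | 18% | 47% |
| 0.7 | 0.8 | 11% | 21% | 45% |
| 0.7 | 0.9 | 6% | 12% | 44% |
| 0.8 | 0.8 | 10% | 18% | 44% |
| 0.8 | 0.9 | 5% | 9% | 42% |

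At a week-1 to pre-test correlation of 0.7, with between-test correlation 0.5-0.7, the chances are about 16-19% per test and 29-33% for at least one. The central range for correlations of 0.9 to 0.7 is about 7-16% and 12-31%. Over all settings tried it is 5-19% and 9-33%.

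Pairing on one test alone gives that test 3% at 0.9, 15% at 0.7 and 23% at 0.5. The 3% and 15% should not be quoted for a composite, which serves both tests but each less closely.

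**5. Precision.** The variance of the planned change comparison falls by about 0-5%. If week-1, pre-test and post-test times are stable ability plus independent noise, the change contains only noise and the gain is nil (simulated variance ratios 0.99-1.04). With baseline adjustment the reduction is roughly 2-13%. A covariate takes the error df from 16 to 15, which raises the squared critical t by 1.1%.

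**The case against.** The strongest reply is that equal-size simple randomisation is valid, contradicts nothing in the plan and needs no repair. That stands. Chance imbalance is already counted in the standard error, and ANCOVA on the pre-test value would deal with regression to the mean whether or not players are paired. Pairing is an improvement, not a correction.

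The second reply is that the benefit rests on unknown correlations. That also stands. Familiarization runs may predict the pre-test poorly, and at 0.5 or below there is little to gain.

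Two stronger readings are tempting, and neither is supported.

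- The Introduction says of fatigue and potentiation that "This balance is affected by a variety of factors, including training experience". A reader might infer that the free draw threatens an imbalance in experience which pairing would cure. The plan gives no spread of experience within this team, and pairing on sprint and T-test times does not balance experience unless the two are related.
- A reader might infer that the week-1 times already exist and cost nothing. The Interventions section starts test data collection in week 2, and the T-test section limits each test to one run for lack of time. Timing week 1 is therefore additional work.

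**Conclusion.** The point holds as a cheap, optional improvement. Under the stated allocation, the chance of a pre-test gap of at least 0.5 SD is 29% on a given test. This figure needs only normality and the 9 versus 9 split. The 44-48% for at least one test also assumes moderate between-test correlation.

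Pairing on the composite would roughly halve the per-test risk or better, to about 7-16%, and bring the risk on at least one test to about 12-31%, if week-1 times correlate 0.9 to 0.7 with pre-test times. The main return is a lower chance of a visibly uneven start. The precision return is small and may be nil for the analysis as planned. It would be wrong to conclude that the present allocation biases the trial.

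**What to change.** **Participants and Interventions.** State that the T-test and 40-m runs in the week-1 familiarization are timed and recorded for all 18 players. Rank the players on the mean of the two standardised times and form nine adjacent pairs. After week 1 and before the interventions begin, someone other than the main researcher makes one random draw per pair, saved as a fixed value, sending one player to each arm. Give the date of the draw. This works only if the week-1 sessions do not depend on arm, which the plan should also say.

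**Statistical analysis.** Include the composite ranking score as a covariate, with its interaction with time, so that the error term reflects the pairing. Alternatively, analyse the post-test value with the pre-test value as covariate. Either costs one error df; fitting pair as a factor would cost eight.

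**Cost.** A few sentences, the timing and recording of week-1 runs, and an allocation that must wait for them. No extra players are needed.

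### Concealment covers only the main researcher, so players and testers may know the arm at the single-run pre-test, and any arm-related effort there enters the group-by-time contrast in full

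*Combined protocol and SAP*

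**What the plan says.** All text is in the combined protocol and SAP.

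- **Who is kept unaware, and until when (Participants).** The sequence is "concealed from the main researcher, responsible for the implementation of the protocols, until the beginning of the interventions". No other role is named. Eligibility is settled before randomization, and the split is 9 and 9.
- **When the intervention starts (Interventions).** The section opens with "We have stipulated that the intervention will last three weeks" and makes familiarization the first of those weeks. It then describes that week as coming "before the initiation of the study to accustom themselves to the physical tests and the protocol procedures", and puts the four protocol sessions in the two weeks that follow.
- **What week 1 contains (Interventions).** "During the first week, the familiarization with the physical tests and the protocol will be performed before the training sessions". The text does not say whether both arms practise the potentiation protocol.
- **When the pre-test takes place (Interventions, Trial Design).** In week 2, "the first moment of collection will be at the at the beginning of first training session". Trial Design adds: "Each group will be tested before and after performing the WU to which they are assigned".
- **Who runs the tests (Trial Design).** "The tests will be applied without a blinded assessor integrating the technical team". No exception is made for the pre-test. The section argues that objective timing equipment makes this unimportant.
- **How often each test is run (Outcomes, T-test).** Once per player, for reasons of time.
- **Analysis (Statistical analysis).** A mixed repeated measures ANOVA at the 5% level. The term that tests the hypothesis is not named.

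**The concern.** Both outcomes are sprint times, so they depend on how hard the player runs and how strongly she is encouraged. Photocells protect the reading of the clock but not the effort behind it. With one run per test, no second attempt dilutes a submaximal one.

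Players cannot be kept unaware of their warm-up once they have done it, but they can be at baseline. The pre-test is therefore the one measurement that could be fully masked, and the stated rule does not secure that. If experimental players ease off slightly in the pre-test, or controls are urged on, the experimental arm later appears to improve more. If experimental players try harder at baseline, a real benefit is hidden. The planned data contain only one baseline per test, so a difference in effort could not be told apart from a chance imbalance.

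**Working it through.** **Step 1. Is the arm hidden at the pre-test? The two readings side by side.**

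| | Intervention starts in week 1 | Intervention starts with the first week-2 warm-up |
|---|---|---|
| Basis in Interventions | Three-week count with familiarization as week 1 | Familiarization precedes the study; protocol sessions follow |
| Main researcher at the pre-test | Concealment has lapsed | Can still be concealed, because the pre-test comes first in the session |
| Testers at the pre-test | Not covered, stated as unblinded | Not covered, stated as unblinded |
| Players at the pre-test | Not covered | Not covered |

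The readings differ only for the main researcher. The gap for players and testers is the same under both.

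**Step 2. How does a baseline shift enter the analysis?** The hypothesis in the Introduction is improvement compared with the control warm-up. In a design with two groups and two times, that is the group-by-time interaction (an inference, since the plan names no term). Its F statistic equals the squared two-sample t on change scores. A numerical check gave 0.0888 for both. Adding 0.5 to one arm's pre-test values moved the between-arm difference in change by 0.5 in size, so the pass-through is 1:1.

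**Step 3. Size.** The plan gives no power calculation, SD or pre-post correlation, so it has no figure to reproduce. Inputs:

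- n = 9 per arm (Participants), so df = 2 × 9 − 2 = 16.
- Significance level 5% (Statistical analysis), taken as two-sided, giving a critical value t(0.975, 16) = 2.120.
- True effect zero.
- d = shift in mean baseline between arms, in SDs of the change score (assumed).

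Noncentrality = d × √(9/2) = 2.121 × d. The probability of a significant result in the direction favoured by the shift is the upper tail of the noncentral t beyond 2.120.

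| d (assumed) | Noncentrality | False result in the favoured direction |
|---|---|---|
| 0 | 0 | 2.5% |
| 0.1 | 0.21 | 3.9% |
| 0.25 | 0.53 | 7.2% |
| 0.5 | 1.06 | 16.8% |
| 1.0 | 2.12 | 51.3% |

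For scale only: if the SD of change were 0.10 s (assumed), d = 0.5 would be 0.5 × 0.10 = 0.05 s.

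**Step 4. Could the analysis repair it?** Here b is the shift in between-player SDs and ρ the pre-post correlation, both assumed. The SD of change is √(2(1 − ρ)) between-player SDs. Regressing the post-test on the pre-test (ANCOVA) lowers the pass-through from b to about ρ × b. Two-sided false-positive rates at b = 0.5 (ANCOVA by simulation, 20,000 runs per setting):

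| ρ | Interaction test | ANCOVA |
|---|---|---|
| 0.5 | 17% | 8% |
| 0.7 | 25% | 15% |
| 0.9 | 61% | 48% |

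Adjustment helps, and helps least where the tests are most repeatable.

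**The case against.** A reader might infer that concealment necessarily ends at or before the pre-test. The documents do not establish this. If the intervention starts with the first week-2 warm-up, the pre-test comes first and the main researcher can remain unaware through it. That objection stands, and the point does not rest on the end date.

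It is also fair to say that nothing in the plan announces the arm to players or testers before the pre-test. The text is silent on when they learn it, which is a gap rather than a plan to disclose. Eligibility precedes randomization, so this is not selection at entry either.

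Trial Design discloses the unblinded assessors and defends the choice. The defence is reasonable for timing error but does not address effort or encouragement.

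The shift sizes are assumptions. At 0.1 SD the favourable error is only 3.9%, and the documents do not indicate which direction is likelier. A reader might also infer that the bias must favour the experimental warm-up, or that no analysis could reduce it. The first is unsupported, and the ANCOVA figures contradict the second.

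Finally, masking the baseline leaves the post-test open. This is true and limits what the remedy achieves, but it does not make an unmasked baseline preferable.

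**Conclusion.** The concern holds as an open route for bias. The concealment clause binds one role until a point that the Interventions section defines inconsistently. Players and testers are outside it on either reading, so a single-run, effort-dependent baseline can be recorded with the arm known.

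The consequence is full pass-through into the difference in change. At assumed shifts of 0.25, 0.5 and 1.0 SD of change, the false-result rate in the favoured direction is 7.2%, 16.8% and 51%, against 2.5%. These figures rest on 9 per arm, a two-sided 5% test of the interaction, no true effect, and shift sizes for which the documents offer no evidence. They show sensitivity and do not predict that bias will occur. The change is worth making because it is cheap and can be made only before the pre-test is run.

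**What to change.** In Participants, replace the concealment clause with wording such as:

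> The allocation list is held by a person other than the main researcher and the testers. It is disclosed to the main researcher, the testers and the players only after both pre-test times of all 18 players have been saved in week 2. Until then, all players follow the same familiarization.

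Randomizing at that moment would serve equally well. In Interventions, define the start of the intervention once, consistently with this rule, and state that week-1 familiarization is identical for all players. Add to the limitations that players know their warm-up at the post-test, so arm-related effort there is not controlled.

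The cost is a few sentences and some waiting: no warm-up can begin until all 18 players have finished both tests, in a session where time already limits each test to one run. No extra player, equipment or analysis is needed. The plan does not say who holds the sequence. Since it is already to be hidden from the main researcher, the role need not require new staff, provided that the holder is not one of the testers.
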